1. INTRODUCTION

The purpose of this reporting and analysis plan (RAP) is to describe the analyses to be included in the Clinical Study Report for Protocol 205207.

All data displays (Tables, Figures & Listings) will use the term “Subject” which reflects CDISC and GSK Data Display Standards terminology.

Revision Chronology:		
2016N273410_00	11-MAY-2017	Original
2016N273410_01	26-SEP-2018	
Amendment 01
 
The protocol had been amended to address feedback from regulatory agencies. The lowest dose level (1.92 mg/kg) in dose escalation phase is removed. To accommodate these changes, the statistical model in dose escalation is revised from Bayesian Logistic Regression Model to modified mTPI and the overall sample size and related analytical methods have been changed. Part 2 stopping criteria has been added for continuous safety monitoring.

2016N273410_02	26-FEB-2020	
Amendment 02
 
The protocol had been amended to address feedback from regulatory agencies, inclusions of items noted in protocol clarification letters, revisions due to discrepancies, revision of study drug related language and other clarifications. DLT evaluable population is included to analysis population to further define Part 1 population.

TMF-12902367	27-AUG-2021	
Amendment 03
 
The protocol had been amended to update pembrolizumab safety, ECI-overdose language, and standard text based on latest IB update for pembrolizumab (2021) and belantamab mafodotin (2021). Addition of the primary analysis at approximately 15 months follow-up from LSLV. Update on planned derived PK parameters and PK/PD analyses, update to data monitoring language, medical monitoring information, and SAE reporting.

TMF-14344600	21-FEB-2022	
Amendment 04
 
The protocol has been amended to provide updates including the addition of the end of study definition Section and continued access to study intervention after the end of the study Section (Post Analysis Continued Treatment [PACT]). Additional contents for risk assessment and mitigation strategy and updated PK and PD Section.

1.1. RAP Amendments

Revision chronology:

RAP Section	Amendment Details
Reporting and Analysis Plan_Study205207_Final_V1 27-OCT-2021	
Reporting and Analysis Plan_Study205207_Amendment_Final_V1 05-AUG-2022	
8.2.1.1 Eye Disorders, Thrombocytopenia, and Infusion Related Reactions	
 Updated onset and duration of first occurrence language
8.7 Clinical Laboratory Analyses	
 Included additional summary of worst case urinalysis results from baseline
8.8.4 Immunogenicity Analyses	
 Included additional summary of immunogenicity incidence
10 Population Pharmacokinetic Analyses	
 Removed dataset specifications language
16.9. Appendix 9 Population Pharmacokinetic (PopPK) Analyses	
 Removed PopPK dataset specifications
16.11.3 Deliverables	
 Updated SAC deliverables for primary and final analyses
16.11.5 Efficacy Tables	
 Updated time-to-event displays to include GSK2857916 2.5 mg/kg + Pembro 200 mg Escalation and GSK2857916 2.5 mg/kg + Pembro 200 mg Overall treatment arms
16.11.6 Efficacy Figures	
 Updated time-to-event displays to include GSK2857916 2.5 mg/kg + Pembro 200 mg Escalation and GSK2857916 2.5 mg/kg + Pembro 200 mg Overall treatment arms
16.11.7 Safety Tables	
 Updated negative ADA results in Anti-GSK2857916 Antibodies (ADA) displays Included Table 3.0094 "GSK2857916 Immunogenicity Incidence and Summary" Included Table 3.0067 "Summary of Worst Case Urinalysis Results Post-Baseline Relative to Baseline"
16.11.14 ICH-Listings	
 Updated time-to-event displays to include GSK2857916 2.5 mg/kg + Pembro 200 mg Escalation and GSK2857916 2.5 mg/kg + Pembro 200 mg Overall treatment arms
16.11.15 Non-ICH Listings	
 The following listings were requested by CPMS to remove: Listing 1.0068 "Listing of Derived Plasma GSK2857916 (ADC) Secondary Pharmacokinetic Parameters", Listing 1.0069 "Listing of Derived Plasma GSK2857916 (Total Antibody) Secondary Pharmacokinetic Parameters", Listing 1.0070 "Listing of Derived Plasma GSK2857916 (cyc-mcMMAF) Secondary Pharmacokinetic Parameters"
16.12. Appendix 12 Example Mock Shells for Data Displays	
 Removed mock shells as per current GSK disclosure process

RAP Section	Amendment Details
Reporting and Analysis Plan_Study205207_Amendment 2_Final_V1 [Refer to Document Date]	
16.11 Appendix 11 List of Data Displays	
• Updated final analysis deliverable to include some additional data displays that were planned for primary analysis only

2. SUMMARY OF KEY PROTOCOL INFORMATION

2.1. Changes to the Protocol Defined Statistical Analysis Plan

There were no changes or deviations to the originally planned statistical analysis specified in the protocol amendment 4 GSK Document Number [TMF-14344600](#) (Dated: 21/FEB/2022).

2.2. Study Objective(s) and Endpoint(s)

Part 1: Dose Escalation

Objectives	Endpoints
Primary Objectives	Primary Endpoints

 To determine safety, tolerability and to establish the recommended Phase 2 dose (RP2D) of the combination of belantamab mafodotin and pembrolizumab in subjects with RRMM 	
 Percent of subjects with adverse events (AEs), changes in clinical signs and laboratory parameters Number of subjects with dose limiting toxicities (DLTs)
Secondary Objectives	Secondary Endpoints

 To evaluate clinical activity of the combination of belantamab mafodotin and pembrolizumab in subjects with RRMM 	
 Overall Response Rate (ORR), defined as the percentage of subjects with a confirmed partial response (PR) or better (i.e., PR, very good partial response [VGPR], complete response [CR] and stringent complete response [sCR]), according to the International Myeloma Working Group (IMWG) Response Criteria [Kumar, 2016].

 To evaluate the pharmacokinetic profile of belantamab mafodotin when administered intravenously in combination with pembrolizumab¹ 	
 Pharmacokinetic (PK) parameters following IV administration as data permit.

 To assess anti-drug antibodies (ADAs) against belantamab mafodotin¹ 	
 Incidence and titers of ADAs against belantamab mafodotin
Exploratory Objectives	Exploratory Endpoints

 To assess Minimal Residual Disease (MRD) in participants who achieve \geqVGPR or better 	
 Minimal Residual Disease (MRD) negativity rate, defined as: the percentage of subjects who are MRD negative in subjects who achieve VGPR or CR

 To characterize the relationship between clinical response and other biologic characteristics 	
 BCMA expression levels on malignant cells, serum sBCMA levels, serum cytokines, and immune cell characterization and their relationship to clinical response (Protein, RNA, DNA analysis)

 To investigate the relationship between genetic variants in the host and response to belantamab mafodotin in combination with pembrolizumab 	
 Possible relationship between host genetic variation and response to belantamab mafodotin in combination with pembrolizumab

 To evaluate the tolerability of belantamab mafodotin in combination with pembrolizumab based on patient 	
 Symptomatic adverse effects as measured by the Patient-reported outcome version of the Common Term Criteria for Adverse Events (PRO-CTCAE)

Objectives	Endpoints
self-report of symptomatic adverse effects	
 Impact of ocular adverse effects on quality of life as measured by the Visual Function questionnaire(s): National Eye Institute 25-item Visual Function Questionnaire (NEI-VFQ-25) and Ocular Surface Disease Index (OSDI)

 To evaluate disease and treatment related symptoms and associated impacts on function and health-related quality of life 	
 Exit Interview

¹ PK and ADA samples for pembrolizumab will be collected and stored during the trial. The analysis will be triggered only in case of unexpected clinical findings.

Part 2: Expansion

Objectives	Endpoints
Primary Objectives	Primary Endpoints

 To assess the clinical activity of the combination treatment with belantamab mafodotin and pembrolizumab in subjects with RRMM 	
 Overall Response Rate (ORR), defined as the percentage of subjects with a confirmed PR or better (i.e., PR, VGPR, CR and sCR), according to the IMWG Response Criteria [Kumar, 2016].
Secondary Objectives	Secondary Endpoints

 To further evaluate the safety of belantamab mafodotin administered in combination with pembrolizumab in subjects with RRMM To further assess the clinical activity of the combination treatment with belantamab mafodotin and pembrolizumab in subjects with RRMM 	
 Number (percent) of subjects with AEs, changes in clinical signs and laboratory parameters Ocular finding on ophthalmic exam Clinical benefit rate (CBR), defined as the percentage of participants with a confirmed minimal response (MR) or better per IMWG Duration of response (DoR), defined as: the time from first documented evidence of PR or better, to the time when disease progression (PD) is documented per IMWG; or death due to PD occurs among subjects who achieve an overall response, i.e. confirmed PR or better Time to response (TTR), defined as: the time between the date of first dose and the first documented evidence of response (PR or better) among participants who achieved a confirmed response of PR or better Time to best response, defined as the time between the date of first dose and the first best documented response (PR or better) among subjects who achieved a confirmed response of PR or better Progression-free survival (PFS), defined as: the time from first dose until the earliest date of PD per IMWG, or death due to any cause Time to disease progression (TTP), defined as: the time from first dose until the earliest date of PD per IMWG, or death due to PD Overall Survival (OS), defined as the time from first dose until death due to any cause

 To evaluate the pharmacokinetic 	
 Pharmacokinetic (PK) parameters following IV

Objectives	Endpoints
profile of belantamab mafodotin when administered intravenously in combination with pembrolizumab ¹	administration as data permit.
• To assess ADAs against belantamab mafodotin ¹	• Incidence and titer of ADA to belantamab mafodotin
Exploratory Objectives	Exploratory Endpoints
• To assess Minimal Residual Disease (MRD) in participants who achieve \geq VGPR or better	• Minimal Residual Disease (MRD) negativity rate, defined as: the percentage of subjects who are MRD negative in subjects who achieve VGPR or CR
• To characterize the relationship between clinical response and other biologic characteristics	• BCMA expression levels on malignant cells, serum sBCMA levels, serum cytokines, and immune cell characterization and their relationship to clinical response (Protein, RNA, DNA analysis).
• To investigate the relationship between genetic variants in the host and response to belantamab mafodotin in combination with pembrolizumab	• Possible relationship between host genetic variation and response to belantamab mafodotin administered in combination with pembrolizumab
• To explore the effect of belantamab mafodotin in combination with pembrolizumab on symptoms and health-related quality of life in subjects with RRMM	• Changes from baseline in symptoms and health-related quality of life as measured by the European Organisation for Research and Treatment of Cancer Quality of Life Questionnaire 30-item Core Module (EORTCQLQ-C30) and European Organisation for Research and Treatment of Cancer Quality of Life Questionnaire 20-item Multiple Myeloma Module (EORTC-QLQ-MY20)
• To evaluate the tolerability of belantamab mafodotin in combination with pembrolizumab based on patient self-report of symptomatic adverse effects	• Symptomatic adverse effects as measured by the PRO-CTCAE • Impact of ocular adverse effects on quality of life as measured by the Visual Function questionnaire(s): NEI-VFQ-25 and OSDI
• To evaluate disease and treatment related symptoms and associated impacts on function and health-related quality of life	• Exit Interview

¹ PK and ADA samples for pembrolizumab will be collected and stored during the trial. The analysis will be triggered if unexpected clinical findings have been identified.

2.3. Study Design

Overview of Study Design and Key Features	
	
 Pembrolizumab
 
Dosing:
 
 -GSK2857916 and pembrolizumab -GSK2857916 first, Pembrolizumab second -If IRR related to GSK2857916, switch to pembrolizumab -Max treatment duration: 1 year
Design Features	
Population: Subjects with relapsed/refractory MM who have undergone stem cell transplant, or are considered transplant ineligible, and who have been previously treated with at least 3 prior lines that include the following: an IMiD (i.e. lenalidomide or pomalidomide), proteasome inhibitor (i.e. bortezomib, ixazomib or carfilzomib) and an anti-CD38 antibody alone or in combination.
 
 • Part 1 Dose Escalation (n = ~ 12 subjects) 
 ◦ Objective: characterize the safety, tolerability, PK, and immunogenicity of escalating doses of belantamab mafodotin in combination with 200 mg pembrolizumab to establish the RP2D. • Part 2 Expansion Cohort(s) (n=~28 subjects) 
 ◦ Objective: Further evaluate the safety, PK, immunogenicity, and clinical activity of belantamab mafodotin at the RP2 dose in combination with 200 mg pembrolizumab identified in Part 1 and to detect if meaningful overall response rate (ORR) can be achieved.
Dosing	
 • Part 1 Dose Escalation 
 ◦ Escalating doses of belantamab mafodotin (2.5 mg/kg, 3.4 mg/kg) will be administered first as an IV infusion once every three weeks (21 days = 1 cycle) in combination with the fixed dose of 200 mg pembrolizumab as an IV infusion to establish the RP2D. 
 ◦ Belantamab mafodotin will be administered first, as an IV infusion, followed by at least 1 hour rest. ◦ Provided there is no infusion related reaction (IRR) warranting a prolonged interval between dosing, pembrolizumab will be administered as second drug over approximately 30 min via IV infusion. • Part 2: Dose Expansion Phase 
 ◦ Subjects enrolled in Part 2 dose expansion phase will be administered belantamab mafodotin at recommended phase 2 dose (RP2D) established in combination with the fixed dose of 200 mg pembrolizumab based on Part 1 outcomes.
Time &	
 • Refer to Appendix 2: Schedule of Activities

Overview of Study Design and Key Features	
Events	
Treatment Assignment	
 This is a non-randomized, single arm, open label, two-part study.
Interim Analysis	
 Part 1: Dose Escalation Phase 
 During the dose escalation, no formal interim analysis is planned for Part 1. Data will be reviewed through data visualization tool to inform dose escalation decisions. The mTPI design will be utilized to guide dose escalation/de-escalation decisions. After the last cohort of subjects in Part 1 complete the DLT observation period, a formal interim analysis will be performed to support the RP2D decision, except for scenarios where RP2D is clearly defined by the toxicity profile. Part 2: Dose Expansion Phase 
 Treatment-related Grade 4 or higher AEs will be continuously monitored starting from when 5 subjects are dosed. If observed toxicity level is significantly higher than 12% at 1-sided alpha of 0.025, the study may be terminated early based on totality of safety data. The 12% threshold is chosen based on 11% Grade 4 or higher AE observed in study BMA117159. Futility analyses for ORR will start when 10 subjects are evaluable. Enrollment may stop if the stopping rule is met based on totality of data. Stopping rules are provided in Section 3.1.2.1 of RAP. Primary Analysis 
 The primary analysis will take place approximately 15 months from the last subject first visit (LSFV). Further details can be referred to in Section 3 of RAP and Section 9.6 of the protocol (version: GSK Document Number TMF-14344600)

2.4. Statistical Hypotheses / Statistical Analyses

2.4.1. Part 1: Dose Escalation Phase

No formal statistical hypotheses are being tested in Part 1. Analysis of the data obtained from Part 1 will only utilize descriptive methods.

2.4.2. Part 2: Expansion Cohort

The primary goal of Part 2 is to characterize clinical activity of the combination and to detect if meaningful response rate (ORR) can be achieved. Based on historical information [[Lokhorst](#), 2015] and clinical judgement, the null hypothesis has been defined as $ORR \leq 40\%$. The alternative hypothesis has been defined as $ORR \geq 60\%$ based on clinically meaningful improvement of 20%.

In Part 2, treatment-related Grade 4 or higher AEs will be continuously monitored starting from when 5 participants are dosed. Based on the 11% Grade 4 or higher AEs observed in the FTIH study (BMA117159), it is considered that the combination treatment has unacceptable toxicity if observed treatment-related Grade 4 or higher AEs is significantly higher than 12% at 1-sided alpha of 0.025.

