3.1.2. Part 2 Dose Expansion Phase

Continuous safety monitoring will be conducted for the expansion cohort starting from when 5 subjects are dosed. The observed number of treatment-related Grade 4 or higher AEs will be compared against the safety stopping rule in [Table 2](#). Enrollment may stop if the safety stopping rule is met based on totality of safety data. For example, if there are 3 events out of 5 dosed subjects, enrollment may stop after review of all safety data; if there is 2 or fewer events out of 5 dosed subjects, enrollment will continue. Operating characteristics for the safety stopping rule are provided in [Figure 1](#). The iSRC will review and may implement Part 2 safety stopping rules, if pre-specified criteria are met. Details of the planned analyses for the iSRC data review meetings, including subject demographic, subject disposition, AE and SAE data, are documented in a separate RAP.

Table 2 Safety Stopping Rules for the Expansion Cohort

Number of dosed subjects	Stop if treatment related Grade 4 or higher AEs larger or equal to this this number
5	3
6-10	4
11-14	5
15-19	6
20-25	7
26-28	8

Figure 1 Operating Characteristics of Safety Stopping Rule for Expansion Cohort

Interim analyses for ORR will start when at least 10 subjects are evaluable as defined in Section 4. Subjects who initially received RP2D in Part 1 may also be included. The observed number of subjects with unconfirmed response of PR or better will be compared with the stopping boundary in Table 3. Enrolment may stop if the stopping rule is met. Final decision will be based on the totality of data. For example, if there are 2 unconfirmed responses out of 10 evaluable subjects, enrolment may stop after review of all available data; if there are 3 or more unconfirmed responses out of 10 evaluable subjects, enrolment will continue. More details of the operating characteristics for futility analysis are provided in Section 3.1.2.1.

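### The 12% limit in the Part 2 safety rule is taken from an 11% rate stated for all Grade 4 or higher AEs, while the rule counts only treatment-related ones; the SAP should use one event definition for both

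*SAP*

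**What the plan says.** The monitored event is the same throughout the SAP. Section 2.4.2 states: "In Part 2, treatment-related Grade 4 or higher AEs will be continuously monitored starting from when 5 participants are dosed". Section 3.1.2 then says: "The observed number of treatment-related Grade 4 or higher AEs will be compared against the safety stopping rule", which is Table 2. The Part 2 interim-analysis entry in section 2.3 also names treatment-related events as what is watched.

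The source of the limit is given twice, each time without the relatedness qualifier. Section 2.3 says: "The 12% threshold is chosen based on 11% Grade 4 or higher AE observed in study BMA117159". Section 2.4.2 opens its sentence with "Based on the 11% Grade 4 or higher AEs observed in the FTIH study (BMA117159), it is considered that the combination treatment has unacceptable toxicity" and closes it with the test: "if observed treatment-related Grade 4 or higher AEs is significantly higher than 12% at 1-sided alpha of 0.025".

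Table 2 gives the stopping counts: 3 at 5 dosed subjects, 4 at 6–10, 5 at 11–14, 6 at 15–19, 7 at 20–25 and 8 at 26–28. Reaching a count does not force a stop. Section 3.1.2 says that enrolment may stop in the light of all the safety data, and that the internal safety review committee (iSRC) reviews the data and may apply the rule.

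**The concern.** Part 2 is single-arm, so the 12% is the only stated statistical benchmark for harm in the expansion cohort. Treatment-related Grade 4 or higher AEs are a subset of all Grade 4 or higher AEs. If the 11% covers events of any cause, the matching treatment-related rate in BMA117159 was 11% or lower. A limit built on the wider rate and applied to the narrower count is then either the same as a like-for-like limit or higher. For a safety rule, higher means more lenient.

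At stake is how early the rule prompts a review, and what a reader may conclude if the boundary is not reached. Section 2.4.2 ties crossing the limit to unacceptable toxicity, so the meaning of the limit should be clear.

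**Working it through.** **Inputs.** The limit of 12% and the one-sided alpha of 0.025 come from sections 2.3 and 2.4.2. The first look at 5 dosed subjects and the counts come from section 3.1.2 and Table 2. The maximum of 28 is the last row of Table 2 and the sample size in section 3.1.2.1.

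**Step 1: reproduce Table 2.** For each n from 5 to 28, take the smallest k with P(X ≥ k | n, 0.12) ≤ 0.025, where X is binomial.

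- n = 5: P(X ≥ 2) = 0.1125 and P(X ≥ 3) = 0.0143, so k = 3.
- n = 10: P(X ≥ 3) = 0.1087 and P(X ≥ 4) = 0.0239, so k = 4.
- n = 28: P(X ≥ 7) = 0.0435 and P(X ≥ 8) = 0.0145, so k = 8.

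All 24 values match Table 2. A null of 11% fails at 7 values of n, and a null of 13% fails at 5. Table 2 contains no arithmetic error, and it rests wholly on the 12%.

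**Step 2: direction.** Let s be the share of the historical 11% that was treatment-related, with 0 < s ≤ 1. The matching historical rate is 11% × s. Keeping the plan's own step from 11% to 12%, the matching limit is 12% × s. A lower null never raises a binomial boundary, so the like-for-like counts are equal to or below those in Table 2.

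**Step 3: size, as an illustration.** The SAP does not give s. Three values are assumed: 100% (limit 12%), 75% (12% × 0.75 = 9%) and 50% (12% × 0.50 = 6%). For each limit the boundary is built as in step 1. The chance of ever crossing it comes from an exact recursion over subjects 1 to 28, with one yes/no indicator per subject and a look after each subject from the fifth.

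| True treatment-related rate | Table 2 (s = 100%) | s = 75%, null 9% | s = 50%, null 6% |
|---|---|---|---|
| 8.25% | 1.4% | 3.8% | 11.8% |
| 15% | 12.3% | 24.3% | 47.8% |
| 20% | 30.7% | 48.2% | 73.1% |
| 40% | 95.4% | 98.3% | 99.7% |

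At a true rate of 20% the shortfall is 48.2 − 30.7 = 17.5 points for s = 75%, and 73.1 − 30.7 = 42.4 points for s = 50%. At s = 75% it falls to 3.8 − 1.4 = 2.4 points at a true rate of 8.25%, and to 98.3 − 95.4 = 2.9 points at 40%. The difference therefore matters over a middle range of true rates. It is nil if s = 100%.

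These limits show sensitivity only. They are not proposed values.

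**The case against.** The strongest reply is that a word was left out. The SAP nowhere says that the 11% is an all-cause rate. Section 2.3 is written in shorthand: it names treatment-related events and then calls the same quantity simply the observed toxicity level. The 11% may be shortened in the same way. Section 2.3 also points to protocol section 9.6 for detail, and that text is not shown. This stands as a real possibility, and in that case Table 2 is right as printed. It does not remove the point. The SAP itself states the derivation, and in section 2.4.2 a single sentence carries the qualifier for the monitored event and omits it for the benchmark. A reader cannot tell which is meant.

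A second reply is that the test is against a fixed 12%, chosen by judgement and already rounded above 11%, for a combination that includes a second active drug. This also stands. The SAP claims toxicity above 12%, not toxicity above historical experience, and it does not promise that the limit equals a like-for-like monotherapy rate. But it does give the 11% as the reason for the 12%, so the reason should refer to the event being counted.

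A third reply is that the rule is non-binding. The iSRC sees AE and SAE data whether or not Table 2 is reached. The probabilities above are therefore chances of reaching a formal trigger, not chances of missing harm.

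Finally, this is a second SAP amendment, concerned with final-analysis displays, so a change now would probably alter no enrolment decision. It would still affect how the rule is described and read in the clinical study report.

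**Conclusion.** The two event definitions differ in the text of sections 2.3 and 2.4.2. On a literal reading the limit, and with it Table 2, is equal to or more lenient than a like-for-like rule.

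A reader might infer that the boundary is definitely set too high. The documents do not support that, because they never state the causality basis of the 11%. A reader might also infer a fixed minimum loss of sensitivity whenever the related share is 75% or less. The check does not bear that out, because the loss depends on the true rate and shrinks at both ends.

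The size stays conditional on the assumed share, on keeping the 12:11 ratio, on one indicator per subject and on a look after every subject. With those assumptions and a true rate of 20%, the crossing probability is 31% under Table 2, against 48% (share 75%) or 73% (share 50%). The non-binding status and the iSRC review soften the practical consequence. The point merits correction because a pre-specified safety criterion depends on it and the check is simple.

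**What to change.** Check the 11% against the BMA117159 data and establish whether it is restricted to treatment-related events. Then reconcile sections 2.3, 2.4.2 and 3.1.2 (with Table 2) so that the benchmark and the monitored count use one stated event definition. If the 11% proves to be treatment-related, say so in sections 2.3 and 2.4.2 and leave Table 2 as it is. If the limit changes as a result of the check, recompute Table 2 and Figure 1 by the same binomial method. Which event definition and which limit are right is for the sponsor's safety review to decide.

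The cost is one look-up in an earlier study, wording in up to three sections and, only if needed, a short recalculation. If the limit came down, the rule would prompt a safety review more often.
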